11.1.2.3. Biopsy

Each patient entered into the trial will have colonic biopsies obtained during flexible sigmoidoscopy/full colonoscopy as follows (see [Table 1](#)):

- One biopsy pair will be taken from the most inflamed area of the left colon. Biopsies will be placed in formalin. These biopsies will be analyzed centrally.
- ONLY if there is suspicion for clinically significant cytomegalovirus (CMV) colitis, one biopsy should be taken from the base of an ulcer to evaluate for histological presence of CMV, but otherwise is not necessary for inclusion in the trial. Analysis will be performed locally.
- Only if histopathologic confirmation of UC is needed to meet trial eligibility, an additional biopsy can be used for histopathologic confirmation of UC (analysis should be performed locally, if possible).
- Only if there is suspicion for dysplasia or malignancy, appropriate biopsies should be taken to exclude malignancy or assess dysplasia. Analysis should be performed locally.

Necrotic areas of ulcerated mucosa should be avoided during biopsy. The original location (colonic segment and endoscopic depth) of biopsy specimens should be clearly indicated.

In all cases the video recordings are to be taken prior to biopsy.

[REDACTED]

[REDACTED]

[REDACTED]

[REDACTED]

[REDACTED]

[REDACTED]

[REDACTED]

[REDACTED]

[REDACTED]

[REDACTED]

12. ASSESSMENTS OF SAFETY

This section describes the procedures for the recording of safety parameters, specific monitoring requirements, and the reporting of adverse events, including adverse events of special interest. A description of the risk-benefit profile of RPC1063 is summarized in [Appendix 3](#) of this protocol

12.1. Safety Parameters

12.1.1. Physical Examination

A complete physical examination will be performed at Screening, M 5, and at the EoT or ET visit, and will include evaluation of heart, lungs, head and neck, abdomen, skin, and extremities, as well as a check for visual symptoms. All significant findings that are present at Screening must be reported on the relevant medical history/current medical conditions eCRF. A check for visual symptoms and a full examination of the skin should be repeated every 6 months. Significant findings made after randomization that meet the definition of an AE must be recorded on the AEs eCRF.

At all other visits following Screening (except M 5/EoT/ET), an interim physical examination will be performed. The interim physical examination will include body systems with previously noted abnormalities and/or those body systems associated with any new complaints from the patient.

12.1.2. Height and Weight

For all patients, height and weight will be measured at Screening.

Height measurements should be made using stadiometry if possible and recorded to the nearest 0.1 cm or ¼ inch. Ideally, the same person should conduct the height measure at each visit in order to minimize variability.

12.1.3. Vital Signs

Systolic and diastolic blood pressure and pulse will be assessed in a sitting position. An automated validated device may be used, if available. In case the cuff sizes available are not large enough for the patient's arm circumference, a sphygmomanometer with an appropriately sized cuff may be used.

Patients will be carefully monitored after the first dose of investigational drug with a 6 hour postdose monitoring period of hourly recording of pulse and blood pressure as described in [Section 12.1.10](#).

12.1.4. Electrocardiogram

The 12-lead digital ECG devices will be provided to each clinical site by the central ECG laboratory for the duration of the trial. Detailed instructions describing the process for recording and transmission of the digital ECGs will be outlined in the trial-specific manual and provided to the site before the start of the trial. Paper versions of ECG tracings recorded at the times specified in the Schedule of Events ([Section 7.1](#)) will be printed and photocopied to preserve the ink if necessary, and kept at the site as source documentation.

An ECG will be performed while resting. The screening ECG report from the central reader must be available to confirm patient eligibility before randomization. Electrocardiograms will be performed before and 6 hours after the first dose of investigational drug administration for all patients on Induction Day 1 while the patient is in the clinic. The 6 hour postdose ECG will be evaluated by the treating physician, with input if needed from a local cardiologist or a central reader to confirm if extended monitoring is required. Additional ECG monitoring will be performed on Days 5 and 8 if cardiac issues are identified on the prior day of dose escalation, as described in [Section 12.1.10](#).

Only clinically significant abnormalities should be reported in the medical history/current medical conditions or the AE eCRF. Clinically significant findings must be discussed with the Medical Monitor before enrolling the patient in the trial.

12.1.5. Ophthalmological Examination

Optical coherence tomography (OCT) will be performed as scheduled in [Table 1](#). All original OCT images are considered source documents that should be made available to the site upon request, or otherwise at the end of the study. If there is a suspicion of new onset macular edema, then general retinal exams, including eye history, visual acuity, and dilated ophthalmoscopy will be obtained. A general ophthalmologist can do the examination, although a retinal specialist would be preferred to do the exams wherever possible. OCT images may be reviewed by an independent panel of ophthalmologists assigned to this trial.

12.1.6. Pulmonary Function Tests

Pulmonary function tests including FEV₁ and FVC measurements will be performed as scheduled in [Table 1](#). In addition, DLCO measurements will be performed at Screening, Visit I 3, Visit M 3, and at the End of Trial or Early Termination visit (see [Table 1](#), footnote p) where locally available. DLCO will not be required at sites where there is no local testing facility. Pulmonary function tests may be performed at a qualified pulmonary function laboratory, respiratory department, or at the clinical trial site. If being performed at the clinical trial site, the Principal Investigator may delegate the performance of this test to any staff member that is qualified to perform the pulmonary function test. If the pulmonary function test results are not within normal range, the results must be verified by a pulmonologist, and potential confounding factors identified. If the patient has a decline in PFT values, the patient should have adequate evaluation as clinically indicated by a pulmonologist as described in [Section 12.2.6](#). Please refer to the American Thoracic Society/European Respiratory Society guidelines for standardization of spirometry and single breath determination of carbon monoxide uptake in the lung ([MacIntyre 2005](#); [Miller 2005a](#); [Miller 2005b](#)).

12.1.7. Dermatological Examination

Dermatological evaluations will be performed by the treating Investigator or designee as part of the physical exam, as scheduled in [Table 1](#). Patients with any suspicious finding noted during the examination will be referred to an appropriately qualified dermatologist for evaluation and treatment, if warranted.

12.1.8. Monitoring of Adverse Events and Serious Adverse Events

Throughout the course of the trial, every effort must be made to remain alert to possible AEs or SAEs. Refer to [Section 12.2](#) for definitions of AEs/SAEs, monitoring and reporting. Refer to [Section 12.2.6](#) for AEs of special interest.

12.1.9. Monitoring of Concomitant Therapy

The use of concomitant medication and procedures will be monitored throughout the trial. Refer to [Section 9.5.3](#) for prohibited concomitant therapies.

12.1.10. Guidelines for Monitoring Patients Taking Their First Dose of RPC1063

On Day 1 of treatment for the IP, careful cardiac monitoring of the patients is required. The Investigator is responsible for monitoring the patient following the first intake of the investigational drug, as well as managing bradycardia symptoms should they occur. The Investigator must review the Baseline predose ECG, pulse, and blood pressure during the 6-hour monitoring period, postdose ECG, and assess discharge status at 6 hours after dosing. Baseline predose ECG should be provided by the site and be available for comparison to the postdose ECG in order to determine if criteria requiring extended monitoring are met.

Resting pulse and blood pressure in the sitting position will be measured before the first dose of investigational drug and every hour for at least 6 hours thereafter (by the Investigator, an assisting nurse, or other medically qualified staff member). When obtaining the pulse and blood pressure before the first dose, the patient should be allowed to rest in a seated position at least 10 minutes before taking measurements. The HR and sitting blood pressure measurements should be repeated 2 additional times (only before the first dose of investigational drug) and the lowest HR and blood pressure will be recorded in the eCRF. The repeat measurements will be made at approximately 2-minute intervals. For the hourly measurements after investigational drug administration, HR and sitting blood pressure will be measured once and recorded in the eCRF. The lowest predose value of sitting heart rate and blood pressure (based on systolic blood pressure) will be recorded in the case report form and serve as baseline for comparison to postdose values.

If possible, patients should receive the first dose of investigational drug before 12:00 pm (noon) in the clinic with or without food. The first dose of investigational drug must be administered in a setting in which resources to appropriately manage symptomatic bradycardia are available. A member of the Investigator team should be available to monitor the patient for the 6-hour monitoring period and will need to report any abnormalities to the Investigator. Atropine and epinephrine or isoproterenol need to be readily available to the site personnel.

If any of the following criteria are met, additional extended monitoring should be instituted until the finding has resolved. Baseline and hourly vital signs measurements (Hours 1 through 6) should be used to assess pulse (criteria 1 and 2 below) and ECG device results should only be used to assess for AV block and QTcF interval (criteria 3 and 4 below).

1. The pulse 6 hours postdose is < 45 bpm
2. The pulse 6 hours postdose is at the lowest value postdose and lower than any other timepoint (suggesting that the maximum PD effect on the heart may not yet have occurred), unless this value is greater than or equal to baseline
3. The ECG 6 hours postdose shows new onset second degree or higher AV block
4. For Adult patients, the ECG 6 hours postdose shows a prolonged QTcF interval (> 450 msec for males, > 470 msec for females)

Should postdose symptomatic bradycardia occur, the treating physician should be notified and he or she should initiate appropriate management, begin continuous ECG monitoring, and continue observation until the symptoms have resolved.

Should a patient require pharmacologic intervention for symptomatic bradycardia, continuous overnight ECG monitoring in a medical facility should be instituted, and the first dose monitoring strategy should be repeated the following day (Day 2). The first dose monitoring strategy should also be repeated at Day 5 or at Day 8 if any cardiac safety issues were observed on the previous Day of dose escalation (see [Table 2](#)).

Patients should have written instruction on when to return to the clinic and a 24-hour contact phone number to call in the event of any new or warranted symptoms (eg, chest pain, dizziness, palpitations, syncope, nausea, vomiting). Patients should be instructed not to drive on the same day after the first dose of investigational drug administration.

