13.2. Statistical Methods

13.2.1. General Considerations

For the purposes of statistical analyses, the IP and the MP will be treated as two independent trials. The analysis of the IP will formally evaluate the efficacy and safety of RPC1063 1 mg vs. placebo as an induction therapy and the analysis of the MP will formally evaluate the efficacy and safety of RPC1063 1 mg vs. placebo as a maintenance therapy.

All efficacy and safety data will be listed by patient. Baseline for the IP is defined as the last observed measurement prior to the Day 1 receipt of investigational drug. Baseline for the MP is defined as the last observed measurement prior to the first dose of investigational drug following randomization into the MP. All safety and efficacy endpoints will be summarized by treatment group.

In general, descriptive summaries will be presented for the efficacy and safety variables collected. Continuous variables will be summarized using number of patients (n), mean, standard deviation (SD), minimum, median, and maximum. Categorical variables will be summarized using frequency counts and percentages.

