As of 20 December 2018, an estimated 4520 subjects have received ozanimod with over 8000 person-years of exposure in a clinical development program including relapsing multiple sclerosis (RMS) and IBD patients. The Phase 1 clinical studies have shown ozanimod to have adequate safety and tolerability, linear PK, and dose-dependent PD effects on lymphocyte counts. The safety and tolerability results from the Phase 2 and Phase 3 studies in RMS, the Phase 2 study in UC, and the ongoing Phase 2 study in CD suggest that ozanimod at doses of 0.46 and 0.92 mg daily is well tolerated and has a good safety profile in subjects with RMS, in subjects with moderately to severely active UC, and in subjects with moderately to severely active CD.

No important risks have been identified associated with ozanimod treatment. Important potential risks based on experience with non-selective sphingosine 1-phosphate (S1P) agonists include symptomatic bradycardia, atrioventricular conduction disorder, liver injury, macular edema, Progressive Multifocal Leukoencephalopathy (PML), Posterior Reversible Encephalopathy Syndrome (PRES), embryofetal toxicity in exposed pregnant females, malignancies, infections, and pulmonary effects.

ptomatic Bradycardia, Atrioventricular Conduction disorder:

Initiation of ozanimod may result in transient reductions in heart rate. In active-controlled MS clinical trials, after the initial dose of ozanimod 0.23 mg, the greatest mean reduction from baseline in heart rate of 1.2 beats per minute (bpm) occurred at Hour 5 on Day 1, returning to near baseline at Hour 6. Heart rates below 40 bpm were not observed. Initiation of ozanimod without dose escalation may result in greater reductions in heart rate.

Ozanimod studies exclude subjects with severe untreated sleep apnea or recent myocardial infarction, unstable angina, stroke, transient ischemic attack, decompensated heart failure requiring hospitalization or Class III/IV heart failure or have a history or presence of second-degree atrioventricular block Type II or third-degree AV block or sick sinus syndrome unless the subject has a functioning pacemaker. Subjects will be excluded from the study if they are being treated with Class Ia or Class III anti-arrhythmic drugs or with 2 or more agents in combination known to prolong PR interval.

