 - < 90 mmHg post-Baseline (denominator will be the number of patients with Baseline SBP ≥ 90)
 - a decrease from Baseline of > 30 mmHg
- DBP:
 - > 90 mmHg post-Baseline
 - > 100 mmHg post-Baseline
 - > 105 mmHg post-Baseline or an increase from Baseline of > 30 mmHg

- >105 mmHg post-Baseline (denominator will be the number of patients with Baseline DBP \leq 105)
- an increase from Baseline of > 30 mmHg
- <50 mmHg post-Baseline or a decrease from Baseline of > 30 mmHg
 - <50 mmHg post-Baseline
 - <50 mmHg post-Baseline (denominator will be the number of patients with Baseline SBP \geq 50)
 - a decrease from baseline of > 30 mmHg
- HR:
 - >100 bpm post-Baseline
 - >120 bpm post-Baseline or an increase from baseline of > 20 bpm
 - >120 bpm post-Baseline (denominator will be the number of patients with Baseline HR \leq 120)
 - an increase from Baseline of > 20 bpm
 - <60 bpm post-Baseline
 - <45 bpm post-Baseline or a decrease from Baseline of > 20 bpm
 - <45 bpm post-Baseline (denominator will be the number of patients with Baseline HR \geq 45)
 - a decrease from Baseline of > 20 bpm

The number and percentage of patients with clinically relevant abnormalities during cardiac monitoring, including those beyond hour 6 on Day 1, will be summarized overall and by hour during pre-defined 6-hour monitoring window on Day 1, as well as overall during cardiac monitoring (Days 1/5/8). The denominator will be the number of patients with observed data at both Baseline and respective post-Baseline timepoint.

Discharge Status eCRF data after receiving extended cardiac monitoring after 6 hours will be summarized by number and percentage of patients. All data reported on the Discharge Status eCRF will be listed, including the reason for extended monitoring.

Box plots will be provided to display the distribution of vital signs results by timepoint on Day 1 up to hour 6, or by visit. In addition, line plots of means and SEs will be created to display the

actual values and change from pre-dose by timepoint on Day 1 up to hour 6. Line plots of means and SEs will also be created to display the actual values and change from Baseline by visit.

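### Day 1 heart-rate baseline is the lowest of three predose readings but each post-dose value is a single reading, so within-arm hourly mean falls are understated by about 0.85 of the reading-to-reading SD

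*Protocol*

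**What the plan says.** Protocol 12.1.10 has heart rate and sitting blood pressure taken before the first dose and then repeated twice, before that dose only. "The repeat measurements will be made at approximately 2-minute intervals", and "the lowest HR and blood pressure will be recorded in the eCRF". That lowest value "will be recorded in the case report form and serve as baseline for comparison to postdose values". For the hourly measurements after dosing, "HR and sitting blood pressure will be measured once and recorded in the eCRF".

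SAP 11.5 repeats the single hourly reading. It summarises hourly change from predose to hour 6 for all patients and counts heart-rate abnormalities that include "a decrease from Baseline of > 20 bpm". The text of 11.5 does not mention the lowest-of-three rule. SAP 11 presents safety results by treatment/cohort and for all RPC1063 patients together, and the text available specifies no between-arm difference for the hourly changes.

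Protocol 13.2.1 words the baseline differently: "Baseline for the IP is defined as the last observed measurement prior to the Day 1 receipt of investigational drug". SAP sections 6 and 11 place the SAP's own definition of Baseline in Appendix 1, which is not in the text available for review.

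For scale, Protocol Appendix 3 reports from the multiple sclerosis trials that "the greatest mean reduction from baseline in heart rate of 1.2 beats per minute (bpm) occurred at Hour 5 on Day 1".

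**The concern.** The two sides of the subtraction are different statistics. The predose side is a minimum, which sits below the patient's average resting rate because of reading noise alone. The post-dose side is one reading, which has no such tilt. Post-dose minus baseline is therefore too high on average, even when the drug does nothing.

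Bradycardia is named first among the adverse events of special interest in Protocol 12.2.6, and the hourly change from predose is the direct description of the first-dose effect. If within-arm values are read as the size of the fall, they will be too small. Cohort 1 has a placebo arm carrying the same shift, so a reader can subtract it. Cohort 2 has none.

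Protocol 13.2.1 does not remove the problem. Its last observed predose measurement cannot be used if only the lowest heart rate was entered in the eCRF. The same recording rule covers blood pressure; this point is confined to heart rate.

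**Working it through.** The plan states no figure for this effect, so there is none to reproduce.

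**Inputs from the documents.** Three predose readings, the lowest recorded, and one reading per post-dose hour (Protocol 12.1.10).

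**Inputs assumed.** Reading-to-reading SD, correlation between readings, and slower variation within the day. The documents give none of these, so ranges are shown.

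**1. Size of the shift.** For three independent normal readings with SD s:

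E[minimum] − mean = −3/(2√π) × s = −0.846 s.

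A single post-dose reading has expectation equal to its mean, so each hourly mean change is shifted by +0.846 s. Other shapes for the readings give similar results: 0.67 s (exponential), 0.80 s (t with 5 df), 0.87 s (uniform).

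**2. Which SD.** If s is the total within-patient SD and readings share a correlation ρ, the shift is 0.846 × √(1 − ρ) × s.

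| ρ | Shift in SD | s = 2 bpm | s = 4 bpm | s = 6 bpm |
|---|---|---|---|---|
| 0 | 0.85 | 1.7 | 3.4 | 5.1 |
| 0.25 | 0.73 | 1.5 | 2.9 | 4.4 |
| 0.5 | 0.60 | 1.2 | 2.4 | 3.6 |
| 0.75 | 0.42 | 0.8 | 1.7 | 2.5 |

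Put another way, take reading noise of 3, 4 or 5 bpm plus slower variation of 5 bpm. The total SD is √(25 + 9) = 5.8, √(25 + 16) = 6.4 or √(25 + 25) = 7.1 bpm. The shift is still 2.5, 3.4 or 4.2 bpm, which is 0.44, 0.53 or 0.60 of the total SD.

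**3. Example.** With reading SD 4 bpm, a true mean fall of 5 bpm is reported as 5 − 3.4 = 1.6 bpm.

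**4. Difference between arms.** The shift is the same in both arms. With a true difference of −0.5 SD, a simulation of 1,000,000 patients per arm returned −0.50 SD.

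**5. Falls over 20 bpm.** Take a 5 bpm drug effect, 5 bpm slower variation and reading SD 4 bpm. The share of patients above the threshold at one hour is:

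- with no reading noise: P(Z > 15/5) = 0.13%
- with the lowest of three as baseline: about 0.4% (numerical integration)
- with the mean of three as baseline: SD of the fall = √(25 + 16 + 16/3) = 6.81, so P(Z > 15/6.81) = 1.4%

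Reading SDs of 3 and 5 bpm give the same order: 0.13% without noise; 0.24% and 0.78% with the lowest of three; 0.68% and 2.5% with the mean.

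**6. Lowest of the six hours.** E[minimum of 6] = −1.27 s. With independent readings and no drug effect, the apparent nadir fall is 1.27 − 0.85 = 0.42 s against the lowest of three, and 1.27 s against the mean of three.

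**The case against.** The strongest objection is that the low baseline does not make every Day 1 summary look safer. That stands. A reader might infer that the count of falls over 20 bpm is biased toward safety. Steps 5 and 6 do not support this: reading noise inflates both the threshold count and the any-hour nadir, and in the scenarios shown it outweighs the low baseline. The mean of three would move both further from the noise-free value.

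A reader might also infer a large effect on the extended-monitoring criterion in Protocol 12.1.10 that exempts an hour-6 pulse at or above baseline. With no drug effect and independent readings, a single reading is at or above the lowest of three in 75% of patients, against 50% for a mean baseline. But the criterion applies only when hour 6 is already the lowest post-dose value. Under the same assumptions, 11.0% of patients meet it with the lowest of three and 15.5% with the mean. The documents do not contradict themselves on this rule, and this point takes no position on it.

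Further objections stand as limits. Every bpm figure rests on an assumed SD. The 1.2 bpm in Appendix 3 comes from other trials whose baseline method is not stated, so it gives scale only. That the SAP analyses the lowest value is inferred from what the protocol says is recorded, because SAP Appendix 1 could not be checked. The bands for lowest Day 1 heart rate and the counts below 45 bpm use no baseline subtraction and are unaffected.

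None of this removes the shift in the hourly mean change.

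**Conclusion.** The concern holds for the within-arm hourly mean change in heart rate on Day 1, and only there. Each such mean fall is understated by about 0.85 of the reading-to-reading SD, or roughly 0.4 to 0.6 of the total within-patient SD once slower variation is counted. At assumed SDs of 2 to 6 bpm this is 1.7 to 5.1 bpm for independent readings, and 1.2 to 3.6 bpm if the SD is the total and readings correlate at 0.5. Over these two ranges the shift is as large as, or larger than, the 1.2 bpm mean reduction quoted in Appendix 3; at a correlation of 0.75 and an SD of 2 bpm it would be smaller.

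The result assumes roughly normal readings and that the recorded lowest value is the analysis baseline. It affects each RPC1063 and placebo column taken alone and all of Cohort 2. It does not affect the Cohort 1 difference in mean change or the absolute heart-rate summaries. It is a cheap improvement to a safety description and does not bear on the efficacy conclusions.

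**What to change.** - Capture all three predose heart rates and use their mean as the analysis baseline for hourly mean change, listing the lowest as well. Confine the change to that summary; it is not offered as an improvement to the count of falls over 20 bpm or to the nadir.
- Protocol Appendix 3 reports 645 adults admitted to Cohort 1 and 367 to Cohort 2, so new eCRF fields come too late for them. Recover the other two readings from source documents where they exist; nothing in the documents confirms that they were kept.
- Where only the lowest is available, show placebo-corrected hourly changes for Cohort 1, and footnote the direction of the bias for Cohort 2 and for all within-arm values.
- State the Day 1 heart-rate baseline in the SAP, and reconcile Protocol 12.1.10 with the general definition in 13.2.1.

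The cost is two eCRF fields for readings already required, some source retrieval, and a few lines of SAP text. The downside is that the analysis baseline would differ from the value used at the site for monitoring. Whether the monitoring criterion keeps its baseline is for the sponsor's clinical team.
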